7.8 Assessment of Efficacy

To assess disease status, imaging will be performed at baseline (within 60 days prior to ASCT) and at 6-8 weeks, 6 months, 12 months, 18 months and 24 months (or until documented disease progression) following the infusion. The choice of imaging will depend on what studies have been most informative in following the subject's disease (i.e., PET, CT scans, MRI, nuclear imaging). If imaging studies are performed at other times after treatment on this study; that data will be collected and information gained will be used for this study.

7.8.1 Measurement of Disease

This study will use the Lugano Classification Lymphoma Response Criteria [74].

The response criteria are defined in APPENDIX II- Revised Response Criteria for Lymphoma:.

The response criteria for lymphomatoid papulosis and primary cutaneous ALCL are defined in Section 18.6 APPENDIX VI: Response Assessment for Cutaneous ALCL/Lymphomatoid Papulosis.

The response criteria for mycosis fungoides and Sezary syndrome are defined in Section 18.7 APPENDIX VII - Response Assessment for Mycoses Fungoides and Sézary Syndrome.

Confidential

8.0 STUDY TREATMENT INFORMATION

8.1 Construction of CD30 Vector

The single chain antibody (scFv) targeting the CD30 molecule was cloned by [name] [60]. The human IgG1 immunoglobulin heavy constant region (hinge-CH2CH3 regions) was added to provide a spacer region between the scFv and the ζ and CD28 ζ endodomain (CAR.CD30) [42]. This spacer region also guarantees the detectability of the CAR on transduced T cells by FACS analysis using a specific monoclonal antibody. The CAR.CD30 was then cloned into the retroviral vector SFG (provided by [name], Cambridge, Massachusetts) that is a Moloney murine leukemia (Mo-MuLV) virus-based vector. A schematic representation of the retroviral construct is shown in Figure 2.

Figure 2 Schematic Representation of SFG.CAR.CD30

8.2 Generation of Transduced Cells

All manufacturing procedures (from Section 8.2.2 onwards) will be performed in our GMP facility located at the address below:

UNC Lineberger Advanced Cellular Therapeutics Facility [name]

The cells will be transduced/manufactured as dictated by Standard Operating Protocols (SOP). Brief summaries are given here.

8.2.1 Source Material

See Section 4.1.1 (procurement).

8.2.2 Activated T Lymphocytes

ATL will be generated using our previously validated SOP. Briefly, PBMC will be activated with anti-CD3 and anti-CD28 antibodies, and then fed with IL-7 and IL-15[77]. Anti-CD3 and anti-CD28 are now available in GMP grade and our validation

studies show improved cell transduction when both anti-CD3 and anti-CD28 antibodies are combined.

8.2.3 Retroviral Production

A retroviral producer line has been generated for the construct at Baylor College of Medicine. A master cell-bank of producer cells has been generated and tested to exclude production of replication competent retrovirus and infection by Mycoplasma, HIV, HBV, HCV and others. Supernatant collected from the master-cell bank was filtered, aliquoted and rapidly frozen and stored at -80°C.

All batches of retroviral supernatant have been tested for sterility and to exclude RCR as issued with the Certificate of Analysis (CoA) and as directed by the SOPs and IND 14688

8.2.4 Transduction

ATL are transduced on day 3-4 after initiation as described previously using recombinant Fibronectin fragment CH-296 (RetronectinTM, Takara Bio, USA) coated plates or bags. Virus is attached to retronectin by incubating producer supernatant in coated plates or bags. Cells are then transferred to virus coated plates or bags.

8.2.5 Ex Vivo Expansion

After transduction transgenic ATL will be expanded feeding them with IL-7 and IL-15 twice a week to reach sufficient numbers as previously described [77]. After transduction a small number of cells will be removed to evaluate for transduction efficiency using flow cytometry.

8.2.6 Freezing

When sufficient number for cell infusion is achieved, cells will be collected and frozen following previously validated SOPs. Cells will be also tested for cytotoxicity against CD30+ tumor cells and CD30 negative cell lines to check receptor function. All lines will be checked for identity, phenotype and microbiological culture and cryopreserved prior to administration according to SOPs. The results will be reviewed by QA prior to issuing a CoA.

8.2.7 Testing

Products that meet study specific release criteria, as detailed on the CoA that accompany each infusion product, will be infused as per Section 4.1.2.

If a positive sterility testing result is reported after the product was infused, the FDA and other relevant parties would be notified as per our manufacturing SOP.

8.3 **Potential Toxicities**

Potential toxicities may be categorized as those related to: infusion of T cells; transduction; cross-reactivity with normal tissues; cytokine release syndrome; neurotoxicity; macrophage activation syndrome and tumor lysis syndrome. In addition to the information presented below, also see Sections 1.5.2., APPENDIX VIII- CRS Toxicity Grading Scale and Management Guidelines.

Retroviral Transduction

There has been concern that even a single retroviral integration can contribute to oncogenesis. Insertional upregulation of cellular proto-oncogenes was the main cause of 5 serious adverse events in two different X-chromosomal linked severe combined immunodeficiency (X-SCID) gene therapy trials. The French study reported 4 cases. Fischer's group replaced the missing common gamma chain (γ c) in X-SCID patients with ex vivo retroviral transduction of autologous stem cells. Four of 11 treated patients developed T-ALL associated with a single retroviral integrant [78, 79]. The integration site of the retrovirus was similar. More recently a case of leukemia has also been reported in a second study in SCID patients conducted in the UK. It is likely that correction of common-gamma chain deficiency and related immunodeficiency syndromes represent special cases. The yc is a shared component of IL-2, IL-4, IL-7, IL-9 and IL-15. Hence it is a crucial component of T- cell proliferation and thymogenesis. A proliferative advantage is expected for progeny of stem cells with functional yc. In female carriers of X-SCID there is a pattern of non-random Xinactivation in T-cells, B-cells, and NK-cells[80]. Moreover a patient with X-SCID developed substantial numbers of T-cells following reversion of the mutant allele in a single hemopoietic stem cell[81]. High efficiency retroviral transduction of human stem cells is difficult to achieve even with GALV pseudotyping. It is likely that in X-SCID, few truly pluripotent stem cells were transduced and the stem cell pool expressing the highest level of transgene (due to integration at a transcriptionally active site) then undergo numerous doublings to restore the entire T-cell compartment. Random mutations caused by this supra-physiological proliferation combined with retroviral integration in a transcriptionally active region led to leukemogenesis.

Our proposal should have a very different risk profile than that reported by Morgan and colleagues and summarized in Section 1.5.2 [45]. Large doses of transduced T-cells (in the order of 10^{10} cells) were administered to patients that received prior lymphodepletion and no leukemogenesis occurred. Although the inclusion of the CD28 endodomain in the CAR may enhance proliferation of transgenic T-cells in response to the CD30 antigen, there is no reason to believe this effect will lead to uncontrolled Tcell expansion. Ex vivo and published in vivo data using several artificial T-cell receptors shows that CD28 sustains limited and temporary expansion over approximately 3 weeks[82]. Our recent clinical trial using CD19-CAR-specific T-cells including the CD28 endodomain also indicates that these T-cells expand significantly for only 2-3 weeks and then they decline without evidence of further expansion [26]. Thereafter, the cells maintain the expression of the transgene, but proliferate further only in the presence of both antigen and exogenous cytokines.

To date, more than 200 patients have received genetically modified cells in clinical trials including patients we have treated on our protocols using retrovirally marked autologous marrow[83] or retrovirally marked EBV-CTLs[64, 84, 85]. In none of these has malignancy caused by retroviral transduction been reported. However, there is a

possibility that the vector could randomly integrate into a site that could lead to leukemogenesis.

Current intensive regimens to treat relapsed lymphoma describe subsequent secondary malignancy rates in excess of 10%[86]. In light of this, the natural history and poor prognosis of advanced lymphoma, and given the entire previous experience with retroviral gene therapy, we feel that the risks of retroviral induced leukemogenesis are small and are justified in this patient group.

Cross-reactivity

CD30 can be expressed by activated T-cells and NK cells. Direct toxicity to these cells due to targeting of their CD30 molecules by transduced cells is possible. In case of this eventuality, a number of therapeutic maneuvers are available. Corticosteroids in doses used to treat graft-versus host-disease (GvHD) will deplete the majority of circulating transduced cells.

CD30 is also expressed on first trimester decidua so there may be a risk of miscarriage in females of child-bearing potential if the cells persist long term. To evaluate this risk we will add a question about miscarriage to our annual follow up evaluation in these patients and report any such events in our annual IND report.

9.0 ADVERSE EVENTS

9.1 Definitions

9.1.1 Adverse Event (AE)

An adverse event (AE) is any untoward medical occurrence (e.g., an abnormal laboratory finding, symptom, or disease temporally associated with the use of a drug) in a subject or clinical investigation subject administered a pharmaceutical product and which does not necessarily have a causal relationship with this treatment. An AE can therefore be any unfavorable and unintended sign (including an abnormal laboratory finding), symptom, or disease temporally associated with the use of a medicinal product, whether or not related to the medicinal product.

Hospitalization for elective surgery or routine clinical procedures that are not the result of an AE (e.g., surgical insertion of central line) need not be considered AEs and should not be recorded as an AE. Disease progression should not be recorded as an AE, unless it is attributable by the investigator to the study therapy.

9.1.2 Suspected Adverse Reaction (SAR)

A suspected adverse reaction (SAR) is any AE for which there is a reasonable possibility that the drug is the cause. Reasonable possibility means that there is evidence to suggest a causal relationship between the drug and the AE. A suspected adverse reaction implies a lesser degree of certainty about causality than adverse reaction, which means any adverse event caused by a drug.

Causality assessment to a study investigational product is a medical judgment made in consideration of the following factors: temporal relationship of the AE to study investigational product exposure, known mechanism of action or side effect profile of study treatment, other recent or concomitant drug exposures, normal clinical course of the disease under investigation, and any other underlying or concurrent medical conditions. Other factors to consider in considering investigational product as the cause of the AE:

- Single occurrence of an uncommon event known to be strongly associated with investigational product exposure (e.g., angioedema, hepatic injury, Stevens-Johnson Syndrome)
- One or more occurrences of an event not commonly associated with investigational product exposure, but otherwise uncommon in the population (e.g., tendon rupture); often more than one occurrence from one or multiple studies would be needed before the sponsor could determine that there is reasonable possibility that the drug caused the event.

• An aggregate analysis of specific events observed in a clinical trial that indicates the events occur more frequently in the investigational product treatment group than in a concurrent or historical control group

9.1.3 Unexpected AE or SAR

An AE or SAR is considered unexpected if the specificity or severity of it is not consistent with the applicable product information (e.g., Investigator's Brochure (IB) for an unapproved investigational product or package insert/summary of product characteristics for an approved product). Unexpected also refers to AEs or SARs that are mentioned in the IB as occurring with a class of investigational product or as anticipated from the pharmacological properties of the investigational product, but are not specifically mentioned as occurring with the particular investigational product under investigation.

9.2 Documentation of Non-Serious Adverse Events or SARs

For non-serious AEs or SARs, documentation shall begin at the time the main study consent form is signed by the subject prior to ATLCAR.CD30 infusion and continues through the 6 week follow-up period after treatment is discontinued. In addition, any AEs or SARs experienced by the subject related to the procurement procedure must also be documented.

Collected information should be recorded in the Case Report Forms (CRF) for that subject. Please include a description of the event, its severity or toxicity grade, onset and resolved dates (if applicable), and the relationship to the study drug. Documentation should occur at least monthly.

10.0 SERIOUS ADVERSE EVENT

10.1 Definition of Serious Adverse Event

An AE or SAR is considered serious if, in the view of either the investigator or sponsor, it results in any of the following outcomes:

- Death;
- Is life-threatening (places the subject at immediate risk of death from the event as it occurred);
- Requires inpatient hospitalization (>24 hours) or prolongation of existing hospitalization;*
- Results in congenital anomaly/birth defect;
- Results in a persistent or significant incapacity or substantial disruption of the ability to conduct normal life functions;
- Important medical events that may not result in death, be life-threatening, or require hospitalization may be considered a serious adverse drug experience when, based upon appropriate medical judgment, that may jeopardize the subject and may require medical or surgical intervention to prevent one of the outcomes listed in the definition. For reporting purposes, also consider the occurrences of pregnancy as an event which must be reported as an important medical event.

*Hospitalization for anticipated or protocol specified procedures such as administration of chemotherapy, central line insertion, metastasis interventional therapy, resection of primary tumor, or elective surgery, will not be considered serious adverse events.

Pregnancy that occurs during the study must also be reported as an SAE.

10.2 Documentation of SAEs or Serious SARs

10.2.1 Timing

After informed consent but prior to initiation of study medications, only SAEs caused by a protocol-mandated intervention will be collected (e.g. SAEs related to invasive procedures such as biopsies, medication washout.

For any other experience or condition that meets the definition of an SAE or a serious SAR, recording of the event must begin from day 1 of study treatment and continue through the 6 week follow-up period after treatment is discontinued.

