	To estimate PFS after infusion of ATLCAR.CD30 post ASCT in subjects with CD30+ lymphoma at high risk for relapse
	To determine the overall survival after infusion of ATLCAR.CD30 post ASCT in subjects with CD30+ lymphoma at high risk for relapse

tem Transplantati TLCAR.CD30	Page 23 of
Exploratory Objectives:	
Study Design:	This study is a multicenter, Phase 1 clinical trial
Primary Endpoint:	Toxicity will be classified and graded according to the National Cancer Institute's Common Terminology Criteria for Adverse Events (CTCAE, version 4.0) and CRS toxicity will be graded according to the toxicity scale outlined in 18.8 (APPENDIX VII- CRS Toxicity Grading Scale and Management Guidelines). The MTD will be based on the rate of dose- limiting toxicity (DLT; see Sections 4.1.3.2 and 4.1.3.3).
Secondary Endpoints:	PFS is defined from day of ASCT to relapse (in subjects with a documented complete response after ASCT) or progression (in subjects with documented stable disease or partial response after ASCT), or death as a result of any cause as per the Revised Response Criteria for Malignant Lymphoma (see APPENDIX II- Revised Response Criteria for Lymphoma) [74].[5].
	Overall survival will be measured from the date of administration of CAR.CD30 transduced ATL to date of death
	Persistence of CAR.CD30 T cells in vivo will be determined by quantitative PCR and flow cytometry in peripheral blood samples
Exploratory Endpoints:	

LCCC1524-ATL Administration of T lymphocytes Expressing the CD30 Chimeric Antigen Receptor (CAR) for Prevention of Relapse of CD30+ Lymphomas after High Dose Therapy and Autologous S A

Page 24 of 154

STUDY SCHEMA

Figure 1 Study Schema

¹ SOC = standard of care.

² See dose levels table for doses to be administered within each cohort.

3 See Time & Events Table for schedule of blood draws post-infusion. Dose limiting toxicity (DLT) will be monitored for up to 6 weeks post infusion. Short-term follow-up will begin after the 6-week safety evaluation and continue for up to 1 year post infusion. See section 7.4 for schedule of long-term follow-up

Page 25 of 154

TABLE OF CONTENTS

SUMMARY OF CHANGES	2
SUMMARY OF CHANGES	4
CONFIDENTIALITY AND INVESTIGATOR STATEMENT	21
STUDY SUMMARY	22
STUDY SCHEMA	24
TABLE OF CONTENTS	25
TABLE OF FIGURES	30
TABLE OF TABLES	30
LIST OF ABBREVIATIONS	31
1.0 INTRODUCTION AND RATIONALE	35
1.1 Study Synopsis	35
1.2 Hodgkin's Lymphoma (HL) Overview	35
1.3 CD30+ Non-Hodgkin's Lymphoma (NHL) Overview	36

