4.1.4 Concomitant Medications/Treatments

Ideally, subjects should not receive other antineoplastic agents for at least 6 weeks post T cells (for purposes of evaluation) however, subjects with progressive disease may receive other therapy if needed at the discretion of their attending physician. If subjects receive other therapy adverse event reporting will cease after the initial 6-week assessments outlined in section 4.2 are completed. These subjects will continue to be monitored after PD according to the Time and Events Table in APPENDIX IV - Abbreviated Follow Up Required After Initiating Alternative Therapy (section 18.4).

If subjects experience PD after the initial 6-week assessment period following the cell infusion has been completed, they should be followed according to the Time and Events Table in APPENDIX IV - Abbreviated Follow Up Required After Initiating Alternative Therapy(section 18.4).

Confidential
Page 55 of 154

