- c. **RCR:** For replication competent retrovirus (RCR) testing, subject blood samples will be collected and stored pre-infusion. The pre-infusion sample will only be tested if the subject develops a long-term gene therapy side effect as described in Section 7.5.2. Additional samples for RCR testing will only be collected and subsequently analyzed in the event that the subject develops a long-term gene therapy side effect as described in Section 7.5.2.
- d. Cytokine Testing: Serum collected before and 3-4 hours after infusion for cytokine testing.
 - 12. Serum from blood drawn for functional studies at baseline and week 6 will be stored for measurement of human anti-mouse antibodies (HAMA). These studies will be performed in the event of a suspected immunologic reaction. See section 7.5.4 for additional details.
 - 13. Data on all adverse experiences/toxicities per CTCAE v4.0 regardless of seriousness must be collected for documentation purposes only for 6 weeks after dosing of the study drug/biologic. Adverse event data collection will cease in subjects that receive any other hemopoietic cell product or receive therapy for relapse of their primary malignancy. Data on disease status will continue to be collected as appropriate.

- a. If CRS signs and symptoms occur (see APPENDIX VIII- CRS Toxicity Grading Scale and Management Guidelines), a serum sample (~1 mL) for IL-6 analysis and 20 mL of blood should be collected before instituting treatment for CRS. Subsequent 20 mL blood samples should be collected once a day for the first 3 days. At the discretion of the sponsor, a daily sample may be requested for an additional 4 days. See section 7.5.6 for additional details.
- b. Serum (~1 mL) and 20 mL of blood should also be collected in the event of serious toxicities that develop that require hospitalization. Subsequent 20 mL blood samples should be collected once a day for the first 3 days. At the discretion of the sponsor, a daily sample may be requested for an additional 4 days. See section 7.5.6 for additional details.
- c. An additional blood sample of approximately 20 mL may be collected if any subject develops an AE or event of clinical significance that is thought to be at least possibly related to the CAR T cells.
 - 14. CoA generated at completion of required studies for production/QA of cells.

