 - 15. ATLCAR.CD30 cells infused after evidence of hematologic recovery post ASCT, see section 4.1.2 for definition of recovery. This will generally occur between 14 and 20 days following infusion of autologous stem cells following high-dose chemotherapy. All subjects will receive their ATLCAR.CD30 infusion at the lead site, the University of North Carolina, Chapel Hill.
 - 16. Patient reported outcomes (PRO) will be measured by the PROMIS Global Health and Physical Function questionnaires and selected items from the NCI PRO-CTCAE (see section 7.6 and APPENDIX V - Patient Reported Outcomes Surveys) (optional). PRO questionnaires will only be offered to adult study participants. PRO questionnaires will first be given at time of screening consent. On the day of infusion, subjects will fill out questionnaires prior to infusion. These questionnaires are optional and may not be given to all subjects.
 - 17. Long Term Follow Up: If a subject develops a delayed adverse event that is related to the trial drug, then more frequent (2-4 times per year) clinical observation may be indicated. Appropriate follow up will be conducted based on a particular subject's prior test results. The investigator will determine the additional testing and sample collection that is needed. New malignancies and delayed adverse events will be recorded during long term follow-up.

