Imaging: Imaging to assess disease status (PET, CT scans, MRI, nuclear imaging) 6-8 weeks following the infusion. The choice of imaging will depend on what studies have been most informative in following the subject's disease. If subject has cutaneous lymphoma see section 7.1.1 for details.

Toxicity: Toxicity will be assessed according to the NCI CTCAE v. 4.0, CRS Toxicity Grading Scale (See APPENDIX VIII- CRS Toxicity Grading Scale and Management Guidelines).

Patient reported outcome questionnaires for adult subjects (optional): PROMIS Global Health Scale, PROMIS Physical Function, and selected questions from NCI PRO-CTCAE

7.3.6 D1 Month 3

Clinical evaluation: history, physical examination, Karnofsky or Lansky performance status.

Laboratory studies:

- CBC with differential and platelets
- CMP: BUN, creatinine, Na, K, Cl, CO2, glucose, calcium, albumin, total protein, total bilirubin, ALT, AST, alkaline phosphatase
- Blood taken for leukemia profile and flow cytometry (mycosis fundgiodes and Sezary syndrome patients only)
- Thyroid function
- Blood Sample for Correlative Studies (see section 7.5)
 - Function and persistence studies
 - Quantitative PCR
 - Genetic analysis (see Section 7.5.5)

Patient reported outcome questionnaires for adult subjects (optional): PROMIS Global Health Scale, PROMIS Physical Function, and selected questions from NCI PRO-CTCAE

7.3.7 D1 Month 6

Clinical evaluation: history, physical examination, Karnofsky or Lansky performance status.

Laboratory studies:

- CBC with differential and platelets
- CMP: BUN, creatinine, Na, K, Cl, CO2, glucose, calcium, albumin, total protein, total bilirubin, ALT, AST, alkaline phosphatase

- Blood Sample for Correlative Studies (see section 7.5)
 - Function and persistence studies
 - Quantitative PCR
 - Genetic analysis (see Section 7.5.5)

Patient reported outcome questionnaires for adult subjects (optional): PROMIS Global Health Scale, PROMIS Physical Function, and selected questions from NCI PRO-CTCAE

Imaging: Imaging to assess progression (PET, CT scans, MRI, nuclear imaging) at 6 months \pm 1 month following the infusion. The choice of imaging will depend on what studies have been most informative in following the subject's disease.

7.3.8 D1 Month 9

Clinical evaluation: history, physical examination, Karnofsky or Lansky performance status.

Laboratory studies:

- CBC with differential and platelets

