11.3 Data Analysis Plans

11.3.1 Safety Analysis of Adverse Event Data

All subjects who received the ATLCAR.CD30 infusion will be included in the safety analysis. Adverse event data and corresponding toxicity grades six weeks after T-cell infusion and during long-term follow-up will be summarized in the form of tables. Incidence tables will be generated to summarize incidence of subjects reporting at least one episode of each specific adverse event, incidence of adverse events causing withdrawal and incidence of serious adverse events. The total number of episodes for each event reported (Frequency Table), the severity and attribution to study therapy of each episode reported (Severity Table and Attribution Table) will also be displayed.

Listings of adverse events by subjects will include the time to onset, the duration of each event, the severity of each event, and the relationship of the event to study therapy, whether it was a serious event, and whether it caused withdrawal. Safety data will be summarized for the overall subject group and by dose levels.

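### Graded AE and SAE recording ends at week 6, so the later toxicity grades that section 11.3.1 plans to tabulate have no defined source

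*Combined protocol and SAP*

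**What the plan says.** **Where recording stops.** For SAEs, section 10.2.1 says that "recording of the event must begin from day 1 of study treatment and continue through the 6 week follow-up period after treatment is discontinued". For non-serious events, section 9.2 starts at the main consent and "continues through the 6 week follow-up period after treatment is discontinued". Footnote 13 to Table 4 says that CTCAE data on all toxicities "must be collected for documentation purposes only for 6 weeks after dosing of the study drug/biologic". The Toxicity row of Table 4 has its last mark at week 6.

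**What the later first-year visits contain.** Sections 7.3.6 to 7.3.9 (months 3, 6, 9 and 12) open with "Clinical evaluation: history, physical examination, Karnofsky or Lansky performance status" and add laboratory tests, correlative samples and optional questionnaires. The week 1 to week 6 visits each have a toxicity item; these four have none. Footnote 3 makes five topics compulsory in the history: new malignancy, neurologic disorder, rheumatologic or autoimmune disorder, hematologic disorder, and possibly product-related infection.

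**Later events.** Section 7.4 and footnote 17 both say: "New malignancies and delayed adverse events will be recorded during long term follow-up". Footnote 17 is attached to the yearly column of Table 4. Note 3 to the Study Schema says: "Short-term follow-up will begin after the 6-week safety evaluation and continue for up to 1 year post infusion".

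**What is to be analysed.** Section 11.3.1 says: "Adverse event data and corresponding toxicity grades six weeks after T-cell infusion and during long-term follow-up will be summarized". It also lists, for each event, onset, duration, severity, attribution and seriousness.

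**Other therapy.** Section 4.1.4 says: "If subjects receive other therapy adverse event reporting will cease after the initial 6-week assessments outlined in section 4.2 are completed". Appendix IV has the same rule.

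**The concern.** The primary objective is safety and tolerability as well as the MTD, and section 1.6 describes this as the first human use of these cells after ASCT. A safety table can show only what sites were told to record. If graded recording stops at week 6, a later table may be empty because nothing was collected, and a reader could take that as absence of toxicity. Visits from month 3 on may also be done by local providers (footnote 1), so what is recorded depends more than usual on explicit instructions. Onset dates, grades and attributions that are not recorded at the time are hard to recover from outside records.

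**Working it through.** The plan gives no figure to reproduce here. The check sets the passages side by side, with one interval calculation.

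**1. Length of the interval.** Recording ends at week 6 and the last first-year visit is at month 12 (week 52). 52 − 6 = 46 weeks; 46/52 = 0.885, so about 88% of the first year.

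**2. What each visit in the interval collects** (Table 4, footnotes 3 and 10, sections 7.3.6 to 7.3.9):

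| Item | Month 3 | Month 6 | Month 9 | Month 12 |
|---|---|---|---|---|
| CTCAE toxicity item | no | no | no | no |
| Footnote 3 history (ungraded) | yes | yes | yes | yes |
| CBC and CMP | yes | yes | yes | yes |
| Thyroid function | yes | no | no | yes |

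Graded toxicity is therefore assessed at 0 of 4 visits, history and CBC/CMP at 4 of 4, and thyroid function at 2 of 4. Pregnancy on study is recorded as an SAE (sections 10.1 and 10.3.2). Adults may also answer optional PRO-CTCAE items. These give the patient's own rating of listed symptoms, not a CTCAE grade, attribution or seriousness.

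**3. A test case.** Take a cardiac hospitalization at week 20.
- Sections 9.2 and 10.2.1 and footnote 13: outside the window.
- Footnote 3 history: not one of the five topics.
- CBC, CMP, thyroid: no field for the event.
- Section 7.4 and footnote 17: covered only if week 20 counts as long-term follow-up, and then with no grade, seriousness or dates required.

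**4. When long-term follow-up starts.** The documents support two readings.
- *After year 1.* The schema note, the placing of months 3 to 12 under the short-term heading of section 7.3, and the position of footnote 17 point this way. Delayed-event recording then does not reach week 6 to month 12. Section 11.3.1, which names only six weeks and long-term follow-up, then promises no table for that interval.
- *From month 3.* Footnote 1 calls the visits from month 3 on long-term follow-up points, and section 7.4 lists sampling at months 3 to 12. Delayed events are then recorded at these visits, but ungraded.

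On both readings the toxicity grades that section 11.3.1 wants from long-term follow-up have no collection instruction behind them.

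**5. Section 4.1.4 and Appendix IV.** Both attach the stop after week 6 to a condition, receipt of other therapy. If recording stops at week 6 for everyone, the condition seems to do no work. One natural reading is that reporting otherwise continues, which sections 9.2 and 10.2.1 and footnote 13 contradict.

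**The case against.** The plan is not blind after week 6, and several stronger conclusions that a reader might draw do not follow.

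- *Delayed events are recorded only after year 1.* Not so. The footnote 3 history is compulsory at months 3, 6, 9 and 12, and the start of long-term follow-up is itself unclear.
- *The plan misses the delayed hematologic toxicity named in the Amendment 6 rationale.* Not so. CBC with differential is drawn at all four visits, new hematologic disorders are a history topic, and section 11.3.2 summarises first-year laboratory data. The same rationale adds that these cytopenias appear manageable and not linked to significant adverse events. Hepatic and thyroid changes are likewise partly visible through CMP and thyroid tests.
- *IND reporting stops at week 6.* Not supported. Section 10.3.3 sets no six-week limit on the sponsor's reporting and requires the investigator to notify SAEs within 24 hours. What is limited is the site recording window in section 10.2.1, on which the recording step in section 10.2.2 rests.
- *Section 4.1.4 proves that reporting was meant to continue.* It can instead be read as keeping reporting in place up to week 6 even when other therapy starts early. That reading also needs reconciling, because footnote 13 says collection ceases once a subject receives therapy for relapse.
- *A probability of missed events can be given.* The documents state no rate for events after week 6, so any such figure would rest on an assumed rate and on complete follow-up.

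The six-week window also matches the DLT window in section 4.1.3, which is a coherent choice for dose finding. What these replies leave standing is narrower: no graded record after week 6, no site recording step for events outside the listed topics, and an analysis section that expects later grades.

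**Conclusion.** The point holds in limited form. Graded AE and SAE recording ends at week 6, and 46 of the first 52 weeks contain no graded assessment at any of four scheduled visits. History in five categories, laboratory values and pregnancies are captured. Other events, of which a cardiac or pulmonary hospitalization is the clearest example, have no site step giving grade, seriousness, attribution and dates. The later grades in section 11.3.1 have no defined source on either reading of when long-term follow-up starts. That conclusion rests on the text alone and on no assumed event rate.

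The DLT window, the CRM and the MTD estimate are untouched. This is an inexpensive improvement that should be made, not a defect that undermines the primary dose-finding result.

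**What to change.** 1. At the existing month 3, 6, 9 and 12 visits, for subjects not on other antineoplastic therapy, record all SAEs and all AEs that are grade 3 or higher or at least possibly related. Give each a CTCAE grade, seriousness, attribution, and onset and resolution dates. Keep all-grade collection to week 6 as it is.
2. Amend sections 9.2 and 10.2.1, footnote 13 and the Toxicity row of Table 4 to match.
3. State in one place when long-term follow-up begins, and align the schema note, footnotes 1 and 17 and section 7.4 with it. Say in section 7.4 which fields are recorded for a delayed adverse event.
4. Reconcile section 4.1.4 and Appendix IV with footnote 13, so that one rule says when AE reporting stops for subjects who start other therapy.
5. Have section 11.3.1 tabulate events up to week 6 and after week 6 separately, and state which events were collected in each period.

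The cost is protocol wording and AE form pages at four visits that already include history, examination, CBC and CMP; no visit or test is added. The downside is some extra data entry and more transplant- or disease-related events to attribute. The threshold in item 1 is a proposal to limit that load. The sponsor could choose another, provided that collection and section 11.3.1 agree.
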